All patients receiving parenteral nutrition are followed by the Clinical Nutrition Service. Eligibility for the trial will be discussed on rounds. Prior historical and physical information, imaging studies, biopsies, and other available specialized tests will be reviewed by the multidisciplinary team experienced in the diagnosis and treatment of parenteral nutrition associated liver disease. Additional biochemical monitoring will be performed as necessary. If the patient's status supports consideration of treatment, the option for non-experimental therapy will be investigated. A similar process will be utilized for self-referrals and potential patients referred from distant healthcare facilities.

Soybean based Fat Emulsion (Intralipid[®] and/or Liposyn[®])

The conventional PN comparison group will be selected from patients previously studied by Andorsky et al.(31) We will study the subset of those patients whose recorded direct bilirubin was ever > 2 mg/dL. Information about these patients will be extracted from the Excel database used for this study and provided to us by the study's Principal Investigator, [name]. A request for research limited to the use of medical records/charts and computer databases was submitted and approved by the Committee on Clinical Investigations on January 17, 2007 (M07-01-0030).

Inclusion Criteria:

Andorsky et al. reviewed medical records of patients who were born at Children's Hospital Boston from 1985 to 1996 and who received a diagnosis of short bowel syndrome at most 30 days after birth (in the neonatal period). Short bowel syndrome was defined as dependence on PN for at least 90 days for diagnosis resulting from congenital intestinal malformations and/or intestinal resection.

Exclusion Criteria:

Patients with incomplete medical records (10 patients briefly seen for a second opinion) were excluded from the Andorsky et al. study. For our study, we will further exclude the subset of patients whose direct bilirubin was never > 2 mg/dL at any time during their follow-up times.

Follow up Study Utilizing Contemporary Historical Controls

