Because both Intralipid® and Liposyn® II are isotonic, both could be infused through either a central or peripheral line. Both products are compatible with parenteral nutrition solutions and were co-infused via y-site. Source container hang times varied during this period, and IFE was either infused from a single container over 24 hours or the container was changed every 12 hours per CDC recommendations. Also during this period, the administration method of PN changed. Prior to 1999, standard 0.2 micron inline filters were used routinely and only PN but not IFE could be infused through them (IFE was infused via y-site beneath the filter). After 1999, 1.2 micron filters became the standard inline filter, allowing for IFE to be filtered along with the PN solution.

Duration of Therapy

Patients remained on either Liposyn® II or Intralipid® until weaned from PN.

Discontinuation of Therapy

Patients at risk for malnutrition or resumption of PN were typically followed by the Clinical Nutrition Service for several months following discontinuation of PN.

ADDITIONAL PREDICTORS OF INTEREST

Since decisions about starting Omegaven® administration will follow a compassionate protocol, we expect that patients receiving Omegaven® will present more severe liver disease than the controls from the historical cohort. Therefore, to correct confounding biases, we anticipate the need to adjust for potential predictors of liver outcomes at baseline. Baseline will be defined as: the date that treatment starts for Omegaven® patients and on the date that patient reached bilirubin levels > 2 for soybean based fat emulsion patients.

The following predictors of liver disease will be considered:

- Baseline direct bilirubin levels.
- Diagnosis of Necrotizing Enterocolitis (vs. any other disease)
- Gender (male vs. female)
- Age (≥ 8 months vs. < 8 months)
- Gestational age
- Birth weight
- Race

To assess patients comparability, we will also descriptively explore trends in direct bilirubin level before the beginning of follow-up (start of treatment date for Omegaven® patients and date in which direct bilirubin level raised to > 2 mg/dL for control patients)

Subgroup Analysis

With exploratory purposes, we will describe safety and/or efficacy of Omegaven® in subgroups of patients including younger (vs. older) patients at baseline, patients who presented with infections (vs. who did not),

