We will also compare nutritional outcomes of the two groups including difference in weight-for- age Z-scores and height-for-age Z-scores from baseline to the moment in which the child starts enteral feeding and to the moment in which the child receives less than 10% of their calories from PN. Comparison between study groups will be performed via t-test or Wilcoxon tests, as appropriate. Using linear regression, we will explore adjustment for baseline alternative predictors of interest. Trends over time in Z-scores will also be explored using regression with repeated measure methods.

Analysis of Efficacy of Omegaven®

The primary outcome to gain preliminary evidence of efficacy will be based on the time from baseline to normalization of bilirubin level, i.e, first time point among three consecutive in which bilirubin is < 2 mg/dL. We do not anticipate that any subject will present a rebound on direct bilirubin after normalization. However, we will describe the cohort with respect to the frequency of rebounds in bilirubin levels.

Crude comparisons of time to normalize direct bilirubin levels between Omegaven® and soybean oil fat emulsion patients will be based on Kaplan-Meier curves and log-rank tests. We will estimate hazard ratios and adjust for potential baseline confounders using Cox-proportional hazard models. For all survival analysis based on non-parametric or semi-parametric methods, we will attribute an infinite time to event (i.e., time to event larger than the largest follow-up time in the whole study population) for subjects who die or receive a liver transplant before bilirubin is normalized. Subjects who die before their bilirubin levels normalize (particularly due to liver failure) have in fact the worse outcome (infinite time to normalize bilirubin) and were not censored before reaching the endpoint of interest. Results of these analysis will be compared with results of analysis excluding subjects who die or are transplanted. Time to reach a total bilirubin of 1.2 will also be compared using survival analysis methods. Analysis of this outcome will proceed as described for direct bilirubin.

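### Age enters the confounder set only as a cut at 8 months, without a stated reason; the adjusted hazard ratio may therefore keep residual confounding by age, which log age would probably reduce at little cost

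*Combined protocol and SAP*

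**What the plan says.** Under Additional Predictors of Interest, the plan explains why adjustment is needed: "we expect that patients receiving Omegaven® will present more severe liver disease than the controls from the historical cohort". It continues: "we anticipate the need to adjust for potential predictors of liver outcomes at baseline". Seven items follow under the words "The following predictors of liver disease will be considered". Age is fourth, written as "Age (≥ 8 months vs. < 8 months". Baseline direct bilirubin, gestational age and birth weight appear in the same list without a cut. No reason is given for 8 months.

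The list feeds the analysis of time to normal bilirubin under Analysis of Efficacy: "We will estimate hazard ratios and adjust for potential baseline confounders using Cox-proportional hazard models". Linear and logistic models are planned for other outcomes. The Data Analysis Plan allows variables to be transformed where appropriate, but sets no rule for age.

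Baseline is "the date that treatment starts for Omegaven® patients and on the date that patient reached bilirubin levels > 2" for the soybean patients. Under Data Collection Methods, date of birth is to be retrieved for the first control cohort, and birth history is collected for Omegaven patients.

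**The concern.** A term that is 0 below 8 months and 1 above treats a 1-month-old and a 7-month-old as the same patient, and likewise a 9-month-old and a school-age child. It adjusts for the share of each group above the cut and for nothing else about age.

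Age differences within the bands are plausible from the design:

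- The listed Omegaven criteria set no age limit. Outside referrals and self-referrals are accepted, and assent from older minors is foreseen.
- First-cohort controls are patients "who received a diagnosis of short bowel syndrome at most 30 days after birth". Contemporary controls must be under 2 years.
- The clocks differ. Controls start when bilirubin first crosses the threshold. Omegaven patients start at treatment, after standard therapies have been used, so possibly later in the disease and at an older age.

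The adjusted hazard ratio for the primary efficacy outcome is at stake. With no randomization, confounding by age that the model does not capture would be read as a treatment effect, in either direction.

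**Working it through.** The plan states no figure for the age-adjusted analysis and no power for the efficacy comparison; its power tables cover safety tests only. There is nothing to reproduce, so the check asks when the cut fails and how badly.

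**When it fails.** Let Z be treatment and g(age) the true effect of age on the log hazard.

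- True model: log h = log h0 + βZ + g(age).
- Fitted model: log h = log h0 + βZ + γ·1(age ≥ 8 months).

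The error carried into β is roughly the difference between groups in mean g(age) within each band, averaged over bands. It is zero if g is flat within bands (a step at 8 months) or if ages are balanced within bands. Otherwise it is not. For example, if g = 0.5·ln(age), patients aged 1 and 7 months differ by 0.5·ln 7 = 0.97 in log hazard, a hazard ratio of about 2.6, and the cut codes both as 0.

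**How badly, under assumptions.** The documents give no age distribution or age effect, so both are assumed here. The simulation used a Cox model with true treatment HR 1, 30 against 30 patients (the largest size in the power tables), 90% events and 3,000 runs per scenario. Ages were log-normal with these medians:

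- A: 4 months (Omegaven) against 2 months (control), with a long upper tail in the Omegaven group.
- B: 8 against 3 months.
- C: 3 against 3 months (balanced).

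Age effects on the log hazard, age in months:

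- log-shaped: 0.5·ln(age/3)
- linear: 0.06 per month
- plateau: 0.2 per month up to 6 months
- step: 0.8 from 8 months

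Share of the crude age bias in the log HR still left after adjustment, scenario A / B (a minus sign means over-correction):

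| True age effect | Crude HR | Cut at 8 months | Linear age | Log age | 3-knot spline on log age |
|---|---|---|---|---|---|
| Log-shaped | 1.33 / 1.56 | 53% / 50% | 37% / 40% | −1% / −2% | −2% / −2% |
| Linear | 1.20 / 1.37 | 37% / 37% | 6% / −2% | 14% / −7% | −11% / −10% |
| Plateau at 6 months | 1.30 / 1.43 | 58% / 59% | 45% / 55% | 10% / 5% | 9% / 3% |
| Step at 8 months | 1.15 / 1.31 | 1% / 0% | 15% / 27% | 25% / 4% | −3% / 5% |

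In the first three rows the HR under the cut was 1.07 to 1.25 when the truth was 1.00, and a two-sided 5% test rejected in 5.9% to 11.6% of runs. With log age the HR was 0.98 to 1.03 and rejection 4.7% to 6.2%. In scenario C every form, including no adjustment, gave HR 1.00 to 1.01.

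**Price in precision.** Mean standard error of the log HR in A and B: cut 0.294 to 0.316, log age 0.298 to 0.335, spline 0.309 to 0.336. Scenario by scenario, log age against the cut runs from 0.298/0.294 = 1.01 to 0.335/0.316 = 1.06. The spline runs from 0.309/0.294 = 1.05 to 0.336/0.310 = 1.08.

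The sign of the bias is a product of the assumptions: older treated patients, and faster normalization with age. Reversing either one reverses it.

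**The case against.** The strongest reply is that this is a modelling preference in an analysis meant only to give preliminary evidence. The list is a candidate set and not a locked model, and transformation of variables is allowed. Both points are fair, but a general line on transformation does not undo a coding written out for one variable and not for its neighbours.

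Three further points stand and shape the fix:

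- Plain linear age is not a safe replacement. It left 37% to 55% of the bias under log-shaped or plateau effects, and it did worse than the cut under a step.
- Continuous age extrapolates where ages do not overlap. If few controls are above 8 months, older Omegaven patients have almost no comparators. The cut then leaves the contrast to be estimated mainly in the younger band. No coding repairs missing overlap; it has to be shown and handled.
- The planned exact stratified analyses need categories, so a cut has a legitimate use there.

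A reader might go further than the documents allow in several ways:

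- **That age is a main confounder.** The plan ranks no predictor, and it stresses severity of liver disease and changes in care over time.
- **That the adjusted hazard ratio is the only protection against confounding.** There is also a contemporary control cohort, a look at bilirubin trends before baseline, and before-and-after safety comparisons within Omegaven patients.
- **That continuous age removes the problem at no cost.** It adds a functional-form assumption, and a spline adds a parameter to a model with seven candidates and perhaps 20 to 30 patients per group.
- **That about 36% is lost.** That figure, 1 − 2/π = 0.363, is the information lost by a median split of a normal covariate. Nothing shows age to be normal or 8 months to be its median, and information loss is not bias.
- **That age is documented exactly everywhere.** Retrieval of date of birth is stated for the first control cohort, whose data were abstracted at two-week intervals. It is not stated for the contemporary cohort.

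**Conclusion.** The point holds in conditional form. The 8-month cut is the stated coding, it is unexplained, and a finer measure of age can be had in at least the Omegaven group and the first control cohort. If the groups differ in age within the bands and age matters there, the adjusted hazard ratio keeps residual confounding that the binary term cannot remove.

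The documents do not allow its size to be stated. Under the assumed imbalances, the cut left 37% to 59% of the crude age bias for smooth or plateauing effects, against at most 14% in absolute value for log age and 11% for a spline. It left about 0% for a true step at 8 months, where log age left up to 25%, and there was nothing to leave when ages were balanced. These percentages illustrate the mechanism and do not estimate the bias in this study. That most first-cohort controls fall below 8 months is a reasonable inference from neonatal diagnosis, but the documents do not say so.

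This is a cheap improvement and not a flaw that invalidates the analysis.

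**What to change.** In Additional Predictors of Interest and the Data Analysis Plan:

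1. Pre-specify baseline age as a continuous term in the Cox, linear and logistic models: log age by default, or a 3-knot spline on log age only if the number of events supports the extra parameter. Fix the choice before outcomes are compared between groups.
2. Report the age distribution by group and its overlap, and repeat the adjusted analysis restricted to the overlapping age range, with the rule for that range set in advance.
3. Keep the 8-month split for descriptive tables, for any exact stratified analysis, and as a sensitivity analysis. If there is a reason for 8 months, state it.
4. Confirm that date of birth is also retrieved for the contemporary control cohort.

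The cost is a few lines of text and, for the first control cohort and the Omegaven group, no new data. Statistically, the price is an assumed functional form and a modestly larger standard error: in the illustrative simulations, about 1% to 6% for log age and 5% to 8% for a spline. The overlap restriction may drop some older Omegaven patients from that one analysis.

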
In a second set of experiments, the same murine model was used to determine whether Omegaven® (Fresenius- Kabi, Bad Homburg, Germany), a commercial fish oil fat emulsion available in Europe, would prevent fatty liver changes by enteral or parenteral routes of administration, and to determine the serum fatty acid profile of these animals. Animals receiving Omegaven® via the oral and intravenous routes had completely normal livers on histology and MRI spectroscopy revealed normal liver fat content. Liver functions tests in orally treated animals were also within the norm, while there were minimal elevations in intravenously treated groups. There was no fatty acid deficiency in these groups as determined by Mead acid (5,8,11-Eicosatrienoic acid) levels in the serum fatty acid analysis. Mead acid is the only polyunsaturated fatty acid of note produced *de novo* by animals and only accumulates under the conditions of essential fatty acid deficiency. Furthermore, arachidonic acid levels were low in Omegaven® treated animals consistent with previous reports. In a third set of experiments, mice were made severely fatty acid deficient. These mice were treated for 10 days with Omegaven® and had complete reversal of their fatty acid deficiency.

Similarly, other investigators studied livers in a newborn pig model and showed that intravenous administration of fish oil, which consists primarily of omega-3 fatty acids, reduced parenteral nutrition-induced cholestasis (22). However, the study was only 3 weeks in duration and long-term effects from administration of omega-3 fatty acids alone were not evaluated. In fact, the idea that one could remove an essential fatty acid from the standard regime of nutritional support by PN has not been accepted. It has been thought that reduction of an essential fatty acid, such as omega-6, during long-term therapy would result in fatty acid deficiency and deterioration of the health of the patient. Our experience to date, as discussed below, demonstrates that the use of Omegaven® as monotherapy does not result in the development of essential fatty acid deficiency and it can actually be used to as monotherapy to treat this deficiency state.

Preliminary Safety and Efficacy Data for Use of Omegaven® in Other Diseases

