As previously mentioned, Omegaven® may be infused in the same manner as conventional fat emulsions through either a central or peripheral line. The emulsion is isotonic. It is compatible with parenteral nutrition solutions and may be co-infused via y-site. Per Infection Control, source containers must be changed every 12 hours and unused product discarded. Omegaven® may be infused through a 1.2micron inline filter.

Dose Modification

Lipid Intolerance

If lipid intolerance develops, defined as serum triglyceride levels > 200 mg/dL, the following will be considered prior to reducing the dose:

- a) If the level was obtained while the patient was receiving a continuous 24-hour infusion of Omegaven®, the total dose should be infused over 20 hours, and a repeat serum triglyceride level obtained prior to resuming the infusion 4 hours later.

b) Other sources of lipid intolerance should be considered and addressed (drugs, renal disease)

If the triglycerides continue to remain high despite the aforementioned interventions, a dosage reduction of 25% of the current dose will be considered.

High Glucose Infusion Rate

Subjects with a high glucose infusion rate (GIR) will have a dose increase up to 1.5 grams/kg/day to allow for a reduction in PN calories from carbohydrates at the discretion of the Omegaven study team and the nutrition service.

Duration of Therapy

Patients will remain on Omegaven® until weaned from PN. Patients may continue monotherapy with Omegaven® as an additional source of calories after the dextrose/protein portion of PN is discontinued

In the event that a patient who has been listed for a liver or liver/intestinal transplant has an organ become available, the participation in this protocol will not preclude them from receiving the transplant.

Disruption of Therapy

In event that Omegaven® cannot be administered (i.e. loss of central venous catheter access, fluid restrictions, need to administer an incompatible medication/blood product), the infusion of Omegaven® may be interrupted and resumed when the conflicting situation is resolved. Some potential interventions that can be used include:

Situation	Possible Solution
Loss of central venous access	Administer via peripheral route
Fluid restriction	Consult with pharmacy to concentrate PN, medications to allow for administration

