Generally, primary safety analyses will be based on time from baseline or 30 days after baseline until two months after patients first reached direct bilirubin levels $< 2\text{mg/dL}$. Baseline will be defined as information collected at the date that treatment starts for Omegaven[®] patients and on the date that patient reached bilirubin levels > 2 for soybean oil fat emulsion patients. Information on mortality and transplant will be collected during the whole treatment with Omegaven[®] and during the whole period for which we have data available in the Andorsky et al. dataset. Primary efficacy analysis will include time from baseline until the patient normalizes bilirubin (presents three consecutive direct bilirubin $\leq 2\text{ mg/dL}$ or a direct bilirubin $\leq 2\text{ mg/dL}$ and weaned from TPN). With exploratory purpose, we will also describe the curve of the several markers for the entire period that Andorsky et al. recorded data.

Outcome/Endpoints

1. Treatment safety

Our primary outcome for treatment safety will be based on patient's essential fatty acid profile. We will compare patients before treatment with Omegaven[®] started and after treatment started (one month after treatment started until treatment stopped) with respect to the frequency with which triene/tetraene ratio > 0.2 at any time. We will also compare the occurrence any event of of hypertriglyceridemia (serum triglyceride $> 400\text{mg/dL}$) between Omegaven[®] and soybean oil fat emulsions. Primary analyses for these and all other safety outcomes will be based on a follow-up time for Omegaven[®] and soybean oil fat emulsions starting 30 days after baseline, i.e., 30 days after treatment started for Omegaven[®] patients and 2 months after the first direct bilirubin level $< 2\text{ mg/dL}$ was recorded. We will also explore comparisons including the time from baseline until the end of follow-up period.

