Omegaven® may be effective in stabilizing or reversing hepatic injury associated with the use of parenteral nutrition. It may allow the patient to continue to receive the majority of his/her caloric intake from parenteral nutrition while advancing on enteral nutrition or awaiting liver or liver/intestinal transplant

Potential Risks of No Treatment

Since Omegaven® will only be offered to those patients for whom no standard therapy is likely to safe and effective, the risks of not being treated are those allowing for the natural history of their disease and associated clinical manifestations to progress. These include fulminate liver failure and death.

Summary – Overall Risk Assessment

Patients will be at some risk inherent in taking a pharmaceutical agent that has not been fully evaluated for long duration treatment. However, the availability of safety data demonstrates no life-threatening risks or toxicities to vital organs or physiologic functions. Prolonged bleeding times and inhibition of platelet aggregation are a potential risk, especially to those patients with an underlying coagulopathy or those being treated with an anticoagulant. The potential benefits of Omegaven® in this patient population are mainly based on the experimental evidence and a single case of dramatic success. However, the study will only be available to those for whom no standard therapy is available or appropriate, or has already failed. The risks and potential benefits will require careful individual assessment by both the investigators and patients. The heterogeneity of clinical manifestations will lead to non-uniform risk-benefit ratios across the eligible patient population.

7. Potential Benefits

The potential benefits of this study apply directly to the patient in question and to possible improvement in the treatment of future patients. If successful, the experimental treatment will provide a safe and effective means of avoiding liver failure requiring transplant or that may lead to death. Thus, the potential complications of surgery or fulminant hepatic failure may be avoided.

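### The general primary safety window closes two months after the first direct bilirubin below 2 mg/dL, while Omegaven continues until the patient is off PN; several safety outcomes have conflicting or truncated windows

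*Combined protocol and SAP*

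**What the plan says.** The section Definition of Primary and Secondary Outcomes/Endpoints opens with a general rule: "Generally, primary safety analyses will be based on time from baseline or 30 days after baseline", ending "until two months after patients first reached direct bilirubin levels" of less than 2 mg/dL. Under Treatment safety it adds: "Primary analyses for these and all other safety outcomes will be based on a follow-up time for Omegaven" and soybean patients starting 30 days after baseline. The rest of that sentence is garbled: where the controls' start should stand, it gives two months after the first value below 2.

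Exposure follows a different clock. Duration of Therapy states "Patients will remain on Omegaven® until weaned from PN", and adds "Patients may continue monotherapy with Omegaven® as an additional source of calories after the dextrose/protein portion of PN is discontinued". The end of the outcomes section likewise ties completion of treatment to being off PN, a contraindication or a family request.

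Two exceptions are explicit. The triene/tetraene comparison covers "one month after treatment started until treatment stopped", and death and transplant are recorded over the whole of treatment. A comparison from baseline to the end of follow-up is planned as exploration only, and that end is not tied to the last infusion.

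Analysis of Safety and Tolerability repeats the 30-day start but gives no end. It makes the primary safety analyses descriptive. Differences between groups in whether an event ever occurred are tested by Fisher's exact test, for exploration.

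**The concern.** Aim 1 is the safety profile of the drug. The risk assessment summary calls Omegaven "a pharmaceutical agent that has not been fully evaluated for long duration treatment". The adult use described did not exceed 4 weeks, and the two infant trials lasted 7 and 14 days. Later on-drug time is therefore where this study adds most, and the general rule leaves that time out for patients who respond early and stay on PN.

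There is also a problem of comparison. The window ends on an efficacy event. The primary efficacy hypothesis is that Omegaven patients reach 2 mg/dL or less sooner than controls. If so, they are observed for less time, and a proportion with any event falls with observation time. The drug could then look safer only because it works faster.

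The trigger is also a single value below 2, whereas the efficacy endpoint requires three consecutive values, or one value plus weaning.

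**Working it through.** **1. The plan's own figure.** Table 5 gives power for between-group safety comparisons. I enumerated two binomials for a two-sided Fisher's exact test at 0.05 with equal groups. For 5% versus 40% this gives 71.6%, 82.2% and 89.3% at 20, 25 and 30 per group, against 72%, 82% and 89% in the table. All 18 cells agree within one point, so the table is not in dispute. It takes one event proportion per group and has no term for length of observation.

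**2. Which outcomes the rule reaches.**

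| Outcome | Wording on its period | Reading |
|---|---|---|
| Triene/tetraene ratio > 0.2 | until treatment stopped | exempt |
| Mortality, transplant | whole treatment | exempt |
| Triglycerides > 400 mg/dL | general rule only | truncated |
| Catheter infections | per follow-up time, no other end given | truncated |
| INR > 2 | listed beside the ratio outcome tied to the intervention period | conflicting |
| Bleeding | compared across treatment periods | conflicting |
| Bloodstream infection | per follow-up time under PN after baseline | conflicting |
| Anaphylaxis | after baseline, no end given | conflicting |

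**3. Share of exposure counted.** Let t be months to the first direct bilirubin below 2 and T months on Omegaven. The documents give neither, so both are assumed. The window runs from month 1 to month t + 2, a length of t + 1 months. On-drug time after month 1 is T − 1. When treatment outlasts the window, the share counted is (t + 1)/(T − 1). With t = 3:

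- T = 6: 4/5 = 80%
- T = 12: 4/11 = 36%
- T = 24: 4/23 = 17%

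Over t from 1 to 6 and T from 4 to 24 months, the share left out runs from 0% (treatment ends inside the window) to (24 − 3)/23 = 91%.

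**4. Proportion with any event.** At a constant rate r per month over m months this is 1 − exp(−rm). With t = 3 and T = 12, m is 4 in the window and 11 on drug:

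| Assumed r | In window | All on-drug time after month 1 |
|---|---|---|
| 0.02 | 7.7% | 19.7% |
| 0.05 | 18.1% | 42.3% |
| 0.10 | 33.0% | 66.7% |

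**5. Comparison with controls.** Assume the same rate, 0.05 per month, in both groups, with first bilirubin below 2 at month 3 on Omegaven and month 8 in controls. The windows are 3 + 2 − 1 = 4 and 8 + 2 − 1 = 9 months. The proportions are 1 − exp(−0.20) = 18% and 1 − exp(−0.45) = 36%. The gap comes from follow-up length alone.

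**6. Patients already on Omegaven.** The inclusion criteria admit them without a bilirubin above 2. If such a patient is below 2 at baseline, t = 0 and the window could be 0 + 2 − 1 = 1 month.

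**The case against.** The strongest reply is that the plan is unclear rather than clearly wrong. The rule is introduced as general, its restatement is garbled, and the analysis section gives no end date. An analyst could fairly take INR, bleeding, bloodstream infection and anaphylaxis to run longer. That stands, and it is why those four need reconciling. It does not rescue triglycerides or catheter infections.

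A reader might infer that the primary safety result as a whole is truncated. It is not: the essential fatty acid profile is the named primary safety outcome, and its triene/tetraene comparison runs until treatment stops.

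A reader might also infer that later events are lost. They are not. Adverse events are reported until study exit, the investigators review cases at least monthly, and the DSMB meets every six months. Trends in triglycerides, fatty acids and coagulation are described over time, and the limitations section promises a before/after comparison of all safety outcomes.

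The protocol's remark that "long-term effects from administration of omega-3 fatty acids alone were not evaluated" should not be used as support. It concerns another group's three-week piglet study, and the worry raised there is fatty acid deficiency, the outcome with the longer window.

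On size, outcomes reported as rates do not change in expectation if the hazard is constant; the shrinkage affects proportions with any event. Patients who never fall below 2, or who wean soon after, lose little or nothing. Rebounds in bilirubin are not anticipated and will be described, so the single-value trigger is a minor point.

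**Conclusion.** The concern holds with limits. As written, the general rule drops on-drug time whenever treatment lasts more than two months past the first direct bilirubin below 2. This is clear for triglycerides above 400 mg/dL and catheter infections, and unresolved for INR, bleeding, bloodstream infection and anaphylaxis. It also makes follow-up length depend on response, which can distort the proportions compared by Fisher's exact test.

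The documents cannot give the size. Under the central assumptions (response at month 3, 12 months on drug, constant 0.05 events per month), 36% of on-drug time after month 1 is counted and 18% rather than 42% of patients show an event. The direction of the between-group distortion rests on the plan's own hypothesis of faster response. If Omegaven patients, expected to be sicker, took longer, it would reverse.

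This should be fixed before analysis. It is not more serious than that, because primary safety is descriptive, no sample size depends on it, and the later data are collected and reviewed.

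**What to change.** In the outcomes section and in Analysis of Safety and Tolerability:

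- State one window for the Omegaven safety outcomes, from day 30 to the last infusion, and remove the competing wording.
- Report events per on-drug patient-month, split before and after the first direct bilirubin below 2.
- Show the two-month follow-up already required after stopping (Discontinuation of Therapy) separately, so that off-drug time does not enter the on-drug rate.
- For comparisons with controls, use the same person-time in both groups, time on PN after baseline, as the plan already does for bloodstream infection. Say how Omegaven given alone after the dextrose/protein portion stops is counted.
- Keep the bilirubin-based window as a secondary analysis.

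The cost is wording and extra table rows. No new data are needed: adverse events are collected until study exit, and the outpatient laboratory schedule continues until the patient is off Omegaven. There are two drawbacks. Reported proportions will be higher, and later laboratory values will be sparser because monitoring may be reduced in stable patients, so late laboratory event rates need that caveat.
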